***These techniques are approved by the CCI under Protocols 2000-200 and 2006-414.***

**Aim 2: To examine the effects of resveratrol on systemic inflammation and/or on adipose tissue macrophages.**

This aim will make use of the **adipose biopsy specimens from Aim 1**. We will therefore examine the effects of resveratrol on macrophage content and activation in adipose tissue, and on systemic markers of inflammation, in **the same n=55 overweight, middle aged** (age 45-65) nondiabetic and diabetic subjects. We will be utilizing the younger 21-44 year old population to assess whether resveratrol has the same beneficial effects in younger subjects.

*We hypothesize that treatment of insulin resistant subjects with resveratrol will lead to reductions in systemic inflammatory markers and reduced content and/or activation of adipose tissue macrophages.* Systemic inflammatory markers to be measured will include TNF-a, IL-6, IL-1b, MCP-1. Adipose tissue macrophages will be isolated from subcutaneous abdominal adipose tissue, and will be quantified by fluorescence activated cell sorting (FACS) analysis. Gene expression of a variety of pro-inflammatory and pro-atherosclerotic factors will be examined by „real-time“ rt-PCR, to determine how resveratrol affects activation of adipose macrophages.

Following administration of resveratrol (n=55) for 28 days, we will examine:

1. Adipose macrophage content, by fluorescence activated cell sorting (FACS) analysis. These data will additionally be confirmed by immunohistochemistry
2. Activation of adipose macrophages, as assessed by expression and production of a variety of pro-inflammatory and pro-atherosclerotic factors, using „real-time“ rt-PCR and immunohistochemistry
3. Plasma levels of cytokines and acute phase reactants

**Adipose biopsy specimens-** Adipose biopsy specimens will be obtained as described above. Suctioned adipose tissue samples will be suspended in PBS and washed with a 40 µm cell strainer. Approximately 1 gram of tissue will be immediately homogenized in Trizol (Life Technologies, Bethesda, MD) with a Tissumizer homogenizer. This technique will ensure optimized yields of mRNA by the inhibition of RNases. The homogenate will be frozen on dry ice, transported to the laboratory and stored at -80°C. Subsequent mRNA extraction and analysis of gene expression will be performed in the Gene Expression Core lab. Remaining fresh adipose biopsy specimens will be immediately processed as described below.

**Collagenase digestion of adipose tissue and cell separation:** The adipose tissue will be digested with collagenase type 1 (Worthington Biochemical, Lakewood, NJ; 0.05gm per 30ml of Hanks Balanced Salt solution with 4% BSA) for 30 minutes at 37°C with intermittent shaking. Adipocytes will be subsequently separated from stromal cells by centrifugation at 2500 rpm for 10 minutes followed by filtration. Macrophages will be separated from stromal cells by CD14+ coated antibody beads

(Dynabeads, Dynal Biotech, Lake Success, NY) by the manufacturer's method. The separated adipocytes and macrophages will be stored in TRIzol.

**Macrophage quantification:** It is possible that the 28 day duration of therapy and effects of resveratrol on adipocyte chemoattractant factors could also impact numbers of macrophages in fat (see below). We will therefore quantify adipose tissue macrophages with immunohistochemistry and/or FACS analysis. To measure macrophage content in adipose tissue by **immunohistochemistry**, samples will be fixed and embedded in paraffin (21). Sections of tissue will be stained for expression of F4/80 (macrophage-specific) with a monoclonal antibody. The total number of nuclei and the number of nuclei of F4/80 expressing cells will be counted for each field. We have also developed a technique to count macrophages by **Fluorescence Activated Cell Sorting (FACS)** analysis. After digestion with collagenase, the pellet of stromal cells will be treated with red blood cell lysing buffer for 5 min followed by incubation with saturating amounts of FITC-labeled human CD14+ antibody (BD Pharmingen) in staining buffer (PBS with 1 mg/ml BSA and 12 mM NaN3, pH 7.2) on ice for 20 min, washed and analyzed immediately by using a FACScalibur flow cytometer (Becton Dickinson, San Jose, CA).

**Quantitative "Real Time" Reverse Transcriptase Polymerase Chain Reaction (rt-PCR):** From the whole fat samples and isolated cells, total RNA will be extracted with TRIzol. cDNA will be made using Superscript First Strand Synthesis System for rt-PCR (Invitrogen Technologies). Gene expression will be quantified using the protocol for the LightCycler instrument (Roche Diagnostics, Indianapolis, IN), using SYBRGreen (Roche Diagnostics, Indianapolis, IN) for fluorescent detection of double-stranded DNA. Plasmid standard curves will be generated to calculate mRNA copy numbers. Gene product specificity will be confirmed by melting curves and by running the PCR products on agarose gels. All reactions will be performed at least three times. The genes of interest will include PAI-1, TNF- $\alpha$ , TGF- $\beta$ , and interleukins 1- $\beta$  and 6 both in whole fat and in macrophages. Expression of these inflammatory factors will thus provide a measure of macrophage activation. In skeletal muscle samples we will quantify *Socs-1/2/3* gene expression, as a documented target of cytokine signaling (44). We will also perform immunohistochemistry and Western blotting to measure *protein levels* of these factors.

**Measurement of circulating cytokines and acute phase reactants:** Plasma samples will be aliquoted into Eppendorff tubes and stored at -20°C. Subsequent measurements of plasma leptin, TNF-a, PAI-1, angiotensinogen, IL-1-b, IL-6, resistin, Acrp30 and SAA will be performed by the Special Assays Core.

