### **General Experimental Conditions:**

On the day of the first pancreatic clamp study the patients will receive a 28 days" supply of resveratrol capsules. The pilot study will be an open-labeled study. The study design requires that all 55 subjects participate in all of the proposed studies, as outlined below. Consequently, additional subjects will be recruited to compensate for those subjects who cannot complete all of the required studies.

Prior to each study, subjects will meet with study personnel to discuss dietary recommendations. Each subject will be instructed to follow a standardized diet plan for three days prior to each of the clamp studies (40% fat: 20% saturated, 10% polyunsaturated, 10% monounsaturated; 35% carbohydrate; 25% protein). Subjects will be asked to refrain from vigorous exercise for three days prior to each clamp study.

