### **Aim 1: To study the effects of resveratrol on age-related insulin resistance**

*We hypothesize that treatment of overweight, middle aged or Type 2 diabetes subjects with resveratrol will result in improved insulin sensitivity, as demonstrated by increased insulin-stimulated glucose uptake and enhanced insulin-mediated suppression of glucose production.*

We will study the following subject group:

- **Overweight and either young or middle aged** (BMI 25-30 kg/m^2, age 21-65) nondiabetic subjects, n=40 diabetic subjects (BMI=25-35) n=15

Each subject will receive a 28 day course of **resveratrol** (n=55). RevGenetics will supply the resveratrol (500 mg capsules; 2 capsules bid) for our proposed studies. A certificate of analysis has been provided by the manufacturer.

A comprehensive study of whole-body insulin action will be undertaken with specially designed „stepped” euglycemic (~90 mg/dl) -hyperinsulinemic clamp studies, both before and after administration of resveratrol.

Thus, we will compare the following parameters under paired conditions in each subject, on day 0 and day 28 of resveratrol treatment:

- a. **hepatic insulin action:** this will be determined as the ability of low infusion rates of insulin (20 mU/m^2.min above basal requirements) to suppress glucose production during the “**low insulin phase**” of the clamp studies.
- b. **peripheral insulin action:** this will be determined as the ability of high infusion rates of insulin (80 mU/m^2.min above basal requirements) to stimulate glucose uptake during the “**high insulin phase**” of the clamp studies.

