All infusions will be stopped at t=360 min. The patient will be given a standard meal and plasma glucose levels will be monitored at 15-30 min intervals for the next one hour. Dextrose infusion will be continued for approximately 45 minutes after the study in order to avoid hypoglycemia. The patient will be discharged after about one hour, provided that his or her condition remains stable.

**Indirect Calorimetry.** A PARVO MEDICS, (TrueOne® 2400 Metabolic Measurements Systems) will be used to estimate rates of carbohydrate and lipid oxidation from T=260-280 in all studies. Twenty minute averaged values for VO2 and VCO2 will be corrected for nitrogen excretion as urinary urea nitrogen measured enzymatically by the method of Kjeldahl (80). Net glucose and lipid oxidation rates will be calculated from indirect calorimetry. The equations used to calculate glucose and lipid oxidation from gas exchange and urinary urea nitrogen excretion have been published (81). Under conditions in which RQ > 1.0, the overestimation of glucose oxidation will be corrected as described (81).

**Analytical procedures –** Plasma glucose will be measured with a Beckman glucose analyzer (Fullerton, CA) by use of the glucose oxidase method. Measurements of plasma insulin, C-peptide, glucagon, and growth hormone are undertaken throughout the studies in order to evaluate the adequacy of the “pancreatic clamp” technique, ie. inhibitory effects of somatostatin on hormone secretion, and uniformity of hormone replacement. All samples will be kept on ice until centrifuged (within 30 min). Plasma samples will then be sorted and handled by the Special Assay Core, and will be stored frozen at -20°C for later assays. Plasma hormone determinations will be performed by radioimmunoassay as previously reported (82), and these determinations will be provided by the Radioimmunoassay Core of the Diabetes Research and Training Center.

**Substrate determination-** Plasma FFA levels will be determined by using an acyl-CoA oxidase based colorimetric kit (Wako, Osaka, Japan) and glycerol will be measured using colorimetric enzymatic methods (83,84). Plasma lactate will be measured by fluorometric enzyme techniques (85).

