#### **Aim 4: To assess the effects of resveratrol on cognition.**

*We hypothesize that resveratrol will enhance cognitive function in middle-aged individuals.* In collaboration with the Department of Neurology we will therefore examine the effects of resveratrol on cognition in **the same n=25 overweight, middle aged** (age 45-65) nondiabetic and diabetic subjects. We will be utilizing the younger 21-44 year old population to assess whether resveratrol has the same beneficial effects in younger subjects.

Following administration of resveratrol (n=25) for 28 days, we will examine:

- **Executive control:** The Attention Network Test is a combination of the cued reaction time (RT) and the flanker task (94,95). The ANT provides estimates of three separate attention networks of alerting, orienting, and executive attention (95,96). Efficiency of the three attentional networks is assessed by measuring how response times are influenced by alerting cues, spatial cues, and flankers (i.e., congruent or incongruent conditions). The task is relatively short and simple so that reliable estimates of the three attention networks can be obtained within 35 minutes for various healthy and pathological populations.
- **Clinical neuropsychology battery:** provides comprehensive assessment of cognitive function (97,98,99). This battery consists of traditional, standardized measures of: a. intelligence, b. memory, c. language, d. executive function, e. visuospatial function and praxis, f. processing speed, and g. mental status. These tests were used in our previous research to demonstrate informative associations between cognitive and motor function (100,101,102).

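### Nothing hides the visit from the microscopy reader or keeps a subject's stored day-0 and day-28 samples in one assay run, so the Aim 2 and Aim 3 biomarker changes are open to reading bias and run error

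*Combined protocol and SAP*

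**What the plan says.** General Experimental Conditions states: "The pilot study will be an open-labeled study". Under Aim 1 all 55 subjects receive resveratrol, and "we will compare the following parameters under paired conditions in each subject, on day 0 and day 28 of resveratrol treatment". The Schedule of proposed clinical studies places fat and muscle biopsies at both clamp visits.

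Aim 2 declares the expected direction: treatment "will lead to reductions in systemic inflammatory markers and reduced content and/or activation of adipose tissue macrophages". Its opening list measures macrophage content by FACS, with immunohistochemistry as confirmation. Its paragraph on macrophage quantification allows immunohistochemistry and/or FACS. For immunohistochemistry, "The total number of nuclei and the number of nuclei of F4/80 expressing cells will be counted for each field"; for FACS, the fresh cells are "washed and analyzed immediately by using a FACScalibur flow cytometer". Aim 3 adds mitochondrial morphology by electron microscopy.

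Most other material is kept. Plasma drawn during the clamp "will be stored frozen at -20°C for later assays". Aim 2 separately freezes plasma for cytokines at -20°C and adipose homogenate for gene expression at -80°C, and embeds the immunohistochemistry samples in paraffin. Aim 3 stores muscle at -80°C. For rt-PCR, Aim 2 specifies plasmid standard curves, melting curves, gel checks and at least three repeats of each reaction.

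The Statistical Analysis section covers data entry, range checks and paired tests. It does not mention specimen coding, reader masking or allocation of samples to assay runs.

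**The concern.** In a single-group before/after comparison, visit and treatment are the same variable. A shift shared by the day-28 readings enters the estimated change in full, and no later analysis can remove it. Masked reading and paired assay are among the few protections such a design still has.

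Two mechanisms are involved.

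- **Reader expectation.** Counting stained nuclei and judging mitochondrial morphology involve judgement, and the hypothesis tells the reader which way the result should go. Manual FACS gating may be exposed in the same way. Plasma assays and rt-PCR are little affected.
- **Run-to-run differences.** These concern plasma cytokines, RNA and protein assays. If runs are grouped by visit, or drift is steady over the 28 days, the mean change is biased. Otherwise run error only adds variance, which costs power.

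These measurements are the whole of Aim 2 and the biopsy part of Aim 3.

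**Working it through.** The plan states no SD of change, assay CV, alpha or power for any biomarker, so there is no figure of its own to reproduce. What follows is illustration only.

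**Inputs from the documents.** n=55 (Aim 2: "Following administration of resveratrol (n=55) for 28 days, we will examine") and n=40 (the completion target under Recruitment Monitoring). The paired t-test in Statistical Analysis is stated for glucose uptake; I take it to extend to the biomarkers.

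**Assumptions.** Two-sided alpha 0.05; no true drug effect; analysis of the log ratio of day 28 to day 0; SD of that log ratio 0.4 or 0.8; a shift of 2%, 5% or 10% in the same direction on every day-28 reading.

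**1. Shift common to all day-28 readings.** Standardised bias d = ln(1 - shift)/SD. The rejection rate comes from the noncentral t distribution with n-1 degrees of freedom and noncentrality d√n.

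| Shift | ln(1 - shift) | d, SD 0.4 | n=40 | n=55 | d, SD 0.8 | n=55 |
|---|---|---|---|---|---|---|
| 2% | -0.0202 | -0.051 | 6% | 7% | -0.025 | 5% |
| 5% | -0.0513 | -0.128 | 12% | 15% | -0.064 | 8% |
| 10% | -0.1054 | -0.263 | 37% | 48% | -0.132 | 16% |

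Worked example: 10% shift, SD 0.4, n=55 gives noncentrality -0.263 × √55 = -1.95 and a rejection rate of 0.48, against a nominal 0.05.

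**2. Independent run error.** If the two visits fall in different runs with independent error of coefficient of variation CV, about 2CV² is added to the variance of the log ratio. With SD 0.4 that variance is 0.16, so the ratio is (0.16 + 2CV²)/0.16:

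- CV 10%: 0.18/0.16 = 1.125
- CV 15%: 0.205/0.16 = 1.281
- CV 20%: 0.24/0.16 = 1.50

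A comparison that had 80% power then has about 75%, 70% and 63%. With SD 0.8 the variance is 0.64, and the increases are only 0.02/0.64 = 3%, 0.045/0.64 = 7% and 0.08/0.64 = 12.5%.

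**3. Which safeguard can reach which assay.**

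| Measurement | Main exposure | Can both visits share a run? |
|---|---|---|
| Immunohistochemistry | Reader | Yes, paraffin blocks |
| Electron microscopy | Reader | Grids can be coded and read together |
| FACS | Gating; instrument drift | No, analysed fresh at each visit |
| Plasma cytokines | Run | Yes, frozen |
| rt-PCR | Run, partly controlled | Yes, frozen |
| Frozen muscle, protein assays | Run | Yes, frozen |

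**The case against.** The strongest reply is that silence is not evidence of bad practice. A reader might infer that the laboratory knows which samples are treated. The documents do not say so: open label describes the treatment, and gene expression and plasma work go to core laboratories that nothing says are told the visit. This stands. The point is that nothing prevents that knowledge.

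A reader might also take frozen storage for later assay as meaning that visits are run separately. It does not; storage is what makes joint assay possible. The text settles neither.

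The rt-PCR standard curves and repeats bear directly on run drift and deserve credit. They are partial: they do not cover differences in RNA extraction or cDNA synthesis, and nothing comparable is stated for plasma cytokines or Western blots.

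Immunohistochemistry is confirmatory in Aim 2's opening list, with FACS leading. That lowers the weight of the count, but the later and/or wording means it could be the only macrophage measure.

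A reader might see an analysis error in counting by field with no stated reduction to one value per subject and visit. That is only missing laboratory detail: the two counts yield a proportion, and a paired test presupposes one value per visit.

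Finally, the Overview and Statistical Analysis mention placebo, and the latter randomization. This conflicts with the single-group design in General Experimental Conditions and Aim 1. Even a placebo arm would not hide the visit from a reader, although a shift common to both arms would cancel between them.

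**Conclusion.** The concern holds as an unprotected risk. As described, the design cannot separate visit-linked reading error or drift from a resveratrol effect on the Aim 2 and Aim 3 specimen measurements, and the plan contains no step to limit either one. Reader bias is the issue for immunohistochemistry, electron microscopy and perhaps FACS gating. Run error is the issue for stored plasma, RNA and protein, and is a bias only when it follows visit or time.

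The size is unknown. The false-positive rates at n=55 run from about 5% (2% shift, log-SD 0.8) to 48% (10% shift, log-SD 0.4), and all rest on assumed shifts and SDs. A reader might take the upper figure as the plan's actual error rate. The documents do not support that, since it requires a 10% shift in one direction on every day-28 reading.

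The principal endpoint, clamp glucose uptake, does not use these readings and is not affected. The change is worth making before specimens are read, because the protection is largely lost once they have been read with the visit known or run in separate batches.

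**What to change.** Add to the laboratory text of Aims 2 and 3:

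1. Code slides, electron-microscopy grids and stored aliquots so that the reader or analyst does not know the visit; hold the key elsewhere until readings are locked.
2. Stain and read, or assay, each subject's two stored specimens (paraffin, plasma, RNA, frozen muscle) in the same run, in random order.
3. For FACS, which cannot share a run, fix the gating rule in advance and gate coded data files without knowledge of visit. This does not remove instrument drift; control or calibration material at each session would address that.

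No extra visits, biopsies or subjects are needed. The cost is relabelling work and a wait until the second visit's sample is in. One limit remains: the day-0 aliquot will have been frozen about 28 days longer than its partner, so same-run assay does not remove any effect of storage time.

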### **Aim 3: To explore the effects of resveratrol on skeletal muscle metabolism and function.**

*We hypothesize that resveratrol treatment will enhance mitochondrial metabolism and improve strength and contractility.* We will examine the effects of resveratrol on mitochondrial content, signaling molecules involved in mitochondrial biogenesis, DNA and protein oxidative damage, and mitochondrial respiration in human skeletal muscle. It is anticipated that mitochondrial ATP production and aerobic muscular function will improve in concert with enhanced insulin sensitivity.

This aim will make use of the **muscle biopsy specimens from Aim 1**. We will therefore examine the effects of resveratrol on muscle mitochondrial function and aerobic muscular function in **the same n=25 overweight, middle aged** (age 45-65) nondiabetic and diabetic subjects. Again, We will be utilizing the younger 21-44 year old population to assess whether resveratrol has the same beneficial effects in younger subjects.

Following administration of resveratrol (n=55) for 28 days, we will examine:

1. Muscle mitochondrial content
2. Muscle mitochondrial function
3. Muscle strength and mobility

**Muscle biopsies:** human skeletal muscle biopsies will be obtained as described above, and stored at -80 °C for analysis of the following:

- mitochondrial content
- signaling molecules involved in mitochondrial biogenesis
- DNA and protein oxidative damage, and
- mitochondrial respiration
- skeletal muscle mitochondrial function (citrate synthase and succinate dehydrogenase activity), content, and morphology by electron microscopy.

**Muscle strength and mobility tests:** will be conducted by our collaborators from the Department of Neurology and assess the following:

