### STATISTICAL ANALYSIS

Data collected from each subject will be edited, entered, verified and entered into a FoxPro data base system in the GCRC. Data quality checking will be performed by computer programs designed to detect errors using accepted ranges, logic checks, and missing values. Outliers will be checked against the original record and correct values will be entered into a final data file. Data from FoxPro files will be transferred into SAS System Version 6.12 (SAS Institute, Cary, NC) for analysis. We shall utilize SAS for all data management and statistical analysis. Descriptive statistics of all the variables at different time points will be derived and reported.

For the specific aims of this study, repeated measurements of several parameters including glucose metabolism and gene expression will be measured in each subject, with the principal endpoint being the rate of whole-body glucose uptake during the final hour of the high insulin clamp. The null hypothesis is that glucose uptake will be equal in each pair of experiments (ie. prior to and following 45 days" treatment with resveratrol or placebo). To determine the changes in glucose uptake between the paired experimental protocols for each subject group, paired Student's t-tests will be performed. For *between-group* comparisons (ie. between the two subject groups randomized to resveratrol or placebo), the principal endpoint will be the difference in whole-body glucose uptake ( $\Delta$ GU) between the 2 experimental conditions (eg. Resveratrol vs. placebo), with null hypothesis that the response to the experimental intervention will be the same in all subject groups. To determine the changes in glucose uptake between the paired experimental protocols for each subject group, analysis of

variance (ANOVA) will be performed by using PROC GLM in the SAS statistical package. Within group effects will be derived from the analysis.

*All values will be presented as the mean +/- SE.*

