### **Protection Against Risk:**

#### **Procedures employed to protect subjects from undue risks include the following:**

- 1) Blood withdrawal: Blood withdrawal during any single study will be limited to less than 190cc and subsequent studies will be separated by at least, a four week interval. The infusion and withdrawal catheters may produce infection or local hematoma, but strict aseptic technique will be observed by the experienced physician performing the procedure.
- 2) 20% glucose: Vein irritation with 20% glucose infusion will be prevented by use of a large-bore antecubital vein.
- 3) Glucagon: Symptoms of mild nausea will be treated with antiemetic medications, if needed.
- 4) Hypoglycemia: All of these studies will be performed by a physician, hypoglycemia will be prevented by blood glucose sampling every 5-10 minutes and if inadvertent hypoglycemia develops can be rapidly treated by glucose infusion.
- 5) Resveratrol: Given data from a number of *in vitro* studies demonstrating that resveratrol can be an inhibitor of various cytochrome P450 enzymes involved in drug metabolism, use of the following drugs will be exclusionary for this study: anti-epileptics, mexilitene, quinidine, cyclorpsorine, tacrolimus, HIV protease inhibitors. Dosages of up to 1000 mg/day have been widely used without reports of adverse effects.

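### Plasma for the Aim 2 circulating markers is held at -20°C with no rule on assay timing, so storage loss between day 0 and day 28 cannot be ruled out or separated from a treatment effect

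*Combined protocol and SAP*

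**What the plan says.** Two places set the plasma storage. Under Aim 2, the paragraph on circulating cytokines and acute phase reactants states: "Plasma samples will be aliquoted into Eppendorff tubes and stored at -20°C". The markers it lists are leptin, TNF-a, PAI-1, angiotensinogen, IL-1b, IL-6, resistin, Acrp30 and SAA. (MCP-1 is named in the aim but not in this list.) In the clamp section, the analytical procedures state: "Plasma samples will then be sorted and handled by the Special Assay Core, and will be stored frozen at -20°C for later assays".

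Tissue is kept colder. Of the adipose homogenate the protocol says "The homogenate will be frozen on dry ice, transported to the laboratory and stored at -80°C", and of muscle, "human skeletal muscle biopsies will be obtained as described above, and stored at -80 °C".

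Aim 1 makes the paired comparison "on day 0 and day 28 of resveratrol treatment", and the schedule of clinical studies agrees. The risk-protection section adds that "subsequent studies will be separated by at least, a four week interval", so 28 days is a minimum gap. The Statistical Analysis section instead describes measurements "prior to and following 45 days" of treatment. The two durations conflict and must be reconciled.

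The General Experimental Conditions describe an open-label study, and Aim 1 gives resveratrol to all 55 subjects. The Overview and the Statistical Analysis section still refer to placebo, but the current design provides no concurrent placebo arm.

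**The concern.** In an uncontrolled before-after comparison, anything that differs systematically between the two visits ends up in the estimated treatment effect. Storage age can be such a factor. Running both samples of a subject in the same assay run removes between-run variation and is a natural choice, but it leaves the day-0 aliquot older by the interval between visits. If an analyte declines at -20°C, the day-0 reading is depressed more than the day-28 reading.

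The direction is fixed. For TNF-a, IL-6 and the other inflammatory markers, where Aim 2 predicts a fall, a real fall would be understated and a null could look like a rise. For a marker where a rise would be read as favourable, the artefact would look like benefit. Acrp30 (adiponectin) is the example: the Background links adiponectin to better insulin sensitivity. A concurrent arm with the same sample handling would allow the shift to be subtracted. This design has none.

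**Working it through.** The documents contain no stability, power or sample-size figure for the plasma markers, so there is nothing of the plan's own to reproduce. What follows is a sensitivity calculation.

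**Inputs from the documents:** storage at -20°C; visits 28 days apart (45 days as a variant, from the Statistical Analysis section); n = 55, made up of 40 nondiabetic and 15 diabetic subjects; paired t-tests.

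**Assumptions:** loss L per 30 days; both samples of a pair assayed together; SD of the log change; two-sided 5% test on the log scale. None of these is stated in the plan.

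**1. Steady (first-order) loss.** Let k = -ln(1 - L)/30. If the day-28 sample has been stored for T days, the day-0 sample has been stored for T + 28. The spurious ratio of day 28 to day 0 is

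exp(-kT) / exp(-k(T + 28)) = exp(28k) = (1 - L)^(-28/30),

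which does not depend on T. An observed ratio is the true ratio times this factor.

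| Loss per 30 days | Factor | True null reads as | True 20% fall reads as | True null, 45-day gap |
|---|---|---|---|---|
| 0% | 1.0000 | 0% | -20.0% | 0% |
| 1% | 1.0094 | +0.9% | -19.2% | +1.5% |
| 5% | 1.0490 | +4.9% | -16.1% | +8.0% |
| 10% | 1.1033 | +10.3% | -11.7% | +17.1% |

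Example: at 5%, 0.95^(-28/30) = 1.0490, and 0.80 × 1.0490 = 0.839, a reading of -16.1%.

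**2. Loss that levels off.** Take f(t) = 1 - A(1 - exp(-t/τ)), with A = 30% and τ = 30 days. The spurious change is f(T)/f(T + 28) - 1. This is +22% if the newer sample is assayed at once, +1.3% if it has been stored 90 days, and +0.06% at 180 days. Under this pattern the assay date decides whether the shift matters.

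**3. Effect on a paired test under a true null.** The shift on the log scale is 28k and the noncentrality is 28k/(SD/√n). With n = 55 and SD 0.4, a 5% loss gives 0.0479/(0.4/√55) = 0.89.

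| n | SD of log change | 1% loss | 5% loss | 10% loss |
|---|---|---|---|---|
| 55 | 0.2 | 6.3% | 41.4% | 94.7% |
| 55 | 0.4 | 5.3% | 14.1% | 43.3% |
| 55 | 0.6 | 5.1% | 9.0% | 22.3% |
| 40 | 0.4 | 5.2% | 11.4% | 32.9% |
| 15 | 0.4 | 5.1% | 7.2% | 14.4% |

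The entries are rejection rates of a nominal 5% test. The excess rejections are apparent rises.

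**4. Equal storage times.** If each sample is assayed after the same T days, the ratio is f(T)/f(T) = 1 for any loss curve, and the shift is zero.

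**The case against.** The strongest reply is that no loss is documented. Nothing in the protocol says that any of these analytes declines at -20°C or is better preserved at -80°C. The size therefore rests on assumed rates that include zero. This stands, and it is why the point is conditional.

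Several stronger readings are tempting, and the documents do not support them:

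- *The two temperatures contradict each other.* They do not. The adipose tissue is homogenised to protect RNA and the muscle is kept for tissue analyses. The comparison shows only that -80°C storage is already in use.
- *Every paired plasma marker is biased.* Glucose is read every 5 to 10 minutes during the clamp. The hormones are measured to check that the clamp worked. Loss, if any, would differ by analyte.
- *Batching cannot remove the problem.* That holds for running a pair together, which the plan does not actually prescribe; the clamp section says only that plasma "will be stored frozen at -20°C for later assays". Equal storage intervals would remove it.
- *The shift is the same however late the pair is run.* That needs steady loss. Step 2 of the working shows otherwise when loss levels off.

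It is also fair to say that, for the Aim 2 prediction of a fall, the shift works against a false claim of benefit. That stands for the inflammatory markers, but not for a rise in Acrp30, and a masked true effect is still an error.

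**Conclusion.** The point holds in limited form. The plan stores plasma for a named set of Aim 2 outcomes at -20°C for an unspecified time, in an uncontrolled before-after design, with no assay-timing rule, storage limit or stability evidence. A storage shift between visits cannot be excluded, and once the data are in it could not be told apart from a drug effect.

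Under a true null the shift runs from 0% to +10.3% for assumed steady losses of 0% to 10% per 30 days. It requires that pairs are assayed together with a 28-day gap. It would be larger with a longer gap, or with fast early loss and prompt assay, and smaller once loss has levelled off.

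A reader might infer that the main result is at risk. The documents do not support that: the principal endpoint is whole-body glucose uptake in the high-insulin phase, not a stored cytokine or hormone level. The weight is that of a secondary-outcome point with an inexpensive remedy.

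**What to change.** In the Aim 2 paragraph on circulating markers, and in the clamp section's analytical procedures for the plasma kept for those assays, change the storage temperature from -20°C to -80°C. Specify single-use aliquots and a log of the freezing and assay dates of each sample. This assumes that any loss is slower at the colder temperature, which the documents do not address.

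The cost is -80°C space at the assay core, whose capacity is not stated, plus some extra tubes and record keeping. The plan already aliquots this plasma.

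Do not rely on storage age as a covariate to correct the result. When pairs are run together, the within-pair age difference is essentially the same for every subject. It is therefore confounded with visit and absorbed into the estimated change. The log serves as documentation, not as an adjustment.

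If -20°C has to be kept, there are two alternatives:

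- Assay both samples of a pair after equal storage times. This removes the shift, but puts the pair in different runs, so between-run variation enters the difference.
- Include quality-control aliquots aged over the same interval in each run, so that loss can be estimated for each analyte. This costs extra assay wells, and it measures the shift rather than preventing it.
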